5. TREATMENT PLAN

5.1 Induction therapy

Will be at treating physician's choice and could include cytarabine-daunorubicin (3+7). High dose cytarabine-mitoxantrone or other appropriate regimens.^{5;24} For patients with MDS or AML patients considered unfit for intensive therapy, it can include treatment with hypomethylating agents.

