5.2 Stem Cell Source and Cell Dose

Within 72 hours after completion of the chemotherapy regimen, and no sooner than 24 hours after administration of the last dose of chemotherapy, umbilical cord graft or haplo-graft will be administered.

Supportive care and premedications for stem cell administration will be governed by current policies of transplant program.

The choice between CBU vs Haplo-graft will be based on availability according to the table below. It may be further influenced by practical issues such as insurance approval etc.

Graft selection algorithm		
1	CBU Unit 5/6 Matched	1 NIMA match with patient
2	CBU Unit 5/6 Matched	Shared IPA target(s) with patient
3	Haplo Identical relative	
4	CBU Unit 4/6 matched	1-2 NIMA matches with patient
5	CBU Unit 4/6 matched	Shared IPA target(s) with patient

5.3 CBU UNIT The CBU unit must supply a minimum of $0.5 \times 10^7/\text{kg}$ and a maximum of $2.5 \times 10^7/\text{kg}$ nucleated cell dose pre-cryopreservation. The unit must match at a minimum of 4 of 6 at HLA-A, -B antigens, -DRB1 alleles with the recipient. Mismatches (0-2) can be at any loci -. Although molecular level typing will be available for the patient and the CBU unit, a match is defined at intermediate resolution for HLA-A and -B and at high resolution for -DRB1. The CBU donor will also have undergone HLA typing of the mother, thus allowing determination of the CBU-IPA and NIMA.

CBU grafts used in this study will be investigational units that meet all criteria for clinical use. Better matching units will be preferred over less matching units as long as the CBU dose exceeds $0.5 \times 10^7 \text{ NBC/kg}$

ALL RECIPIENTS SHOULD HAVE TESTING FOR CLASS I AND CLASS II HLA ANTIBODIES. IF ANTIBODIES ARE PRESENT, CBU SHOULD BE CHOSEN THAT ARE NOT TARGETED. THIS MAY REQUIRE DQ AND DP TESTING OF THE CBU.²⁵⁻²⁷

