7.4 Response Assessment

A bone marrow examination to document response must be performed in all patients on or before Day 60. Physicians should consider earlier bone marrow exams in patients whose peripheral blood counts are not recovering or recovering sluggishly. Subsequent treatment (consolidation, salvage therapy, etc) will be at the discretion of the treating physician.

Patients will continue to be followed for survival, and disease status. Samples for correlative studies will be collected, if possible at 2 month intervals after day 60, until one year after treatment.

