9.0 CRITERIA FOR STUDY EVALUATION

- Responses must be maintained with no evidence of AML/MDS for more than four weeks. If chemotherapy continues, there can be no evidence of relapse within four weeks. Response assessments will require a bone marrow aspirate to be performed. In the event of a dry tap or an aspiration that is inadequate for interpretation, a bone marrow biopsy is required for response assessment.
- **Complete Remission (CR):** Complete remission is defined as all of the following:

- Peripheral Blood Counts:
 - Absolute neutrophil count $\geq 1000/\mu\text{L}$
 - Platelet count $\geq 100,000/\mu\text{L}$

- No leukemic blasts in the peripheral blood
 - Adequate erythroid recovery so that RBC transfusions are not necessary
- Bone Marrow:
 - Adequate cellularity
 - No Auer rods
 - < 5% blast cells
- No extramedullary leukemia (such as CNS or soft tissue involvement)

OR

- Complete Response with Incomplete Platelet Recovery (CRp): CRp satisfies all CR criteria except platelets < 100,000/ μ L, but platelet transfusions are not necessary
- **Partial Remission (PR):** Must meet all criteria of a CR except that the bone marrow may contain 5%-24% blasts
- **Treatment Failure:** Failure to achieve a CR (by 60 days after initial induction therapy started)
 - Treatment Failure Due to Resistant Disease:
 - Patients treated appropriately
 - Survived > 30 days after therapy began.
 - Failed to achieve remission due to persistent AML as determined by peripheral blood and bone marrow aspirate and biopsy.
 - Treatment Failure Due to Death of the Patient:
 - Patient died within 30 days of starting protocol therapy.
 - Record whether the patient died with or without evidence of persistent leukemia as determined by peripheral blood and bone marrow aspirate and biopsy.
- **Relapse** - Any of the following, occurring after either CR, CRp, or PR:
 - The reappearance of circulating blast cells not attributable to “overshoot” following recovery from myelosuppressive therapy
 - > 5% blasts in the marrow, not attributable to another cause (e.g., CSF, bone marrow regeneration)
 - Development of extramedullary leukemia

- **Toxicities will be followed using CTCAE criteria.**
Most toxicities will be attributable to the chemotherapy. Toxicity attributed to the cell infusions may include occurrence of GVHD and unexpected duration of myelosuppression. Severity of myelosuppression (hematologic toxicity) will not be taken into account.
- **Time to neutrophil recovery:**

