The first of three consecutive days with ANC $>5 \times 10^9/L$.
- **Time to platelet recovery;**
Platelet recovery is reported when the platelet count is $\geq 20 \times 10^9/L$ seven days after platelet transfusion and is maintained for three consecutive lab values obtained on different days.
- **Treatment Related Mortality**
Considered any death that cannot be explained by persistence, relapse or progression of the underlying malignancy once the preparative regimen starts.
- **Acute GVHD**
Acute GVHD will be scored according to the criteria proposed by Przepiorka et al.²⁸
Risk score for acute GVHD will be further assigned based on recent publication by Mac Millan et al.²⁹
Chronic GVHD will be scored according to the consensus criteria.³⁰

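### The treatment-related mortality definition has an unclear start and no end, so it mixes protocol deaths with deaths from later off-protocol treatment

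*Combined protocol and SAP*

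**What the plan says.** Section 9.0 gives the TRM rule in one sentence: "Considered any death that cannot be explained by persistence, relapse or progression of the underlying malignancy once the preparative regimen starts". It states no closing date, no stop at a new treatment and no denominator.

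The treatment before the graft goes by other names. Section 5.1 calls it induction therapy, chosen by the treating physician. Section 5.2 times the graft "Within 72 hours after completion of the chemotherapy regimen, and no sooner than 24 hours after administration of the last dose of chemotherapy".

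On what follows, Section 7.4 says: "Subsequent treatment (consolidation, salvage therapy, etc) will be at the discretion of the treating physician". The same section adds: "Patients will continue to be followed for survival, and disease status". Section 11.1 repeats that follow-up for patients who have left protocol therapy. Neither section gives an end date for survival follow-up.

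Section 10.1 counts a patient as treated only once cells are infused, and replaces enrolled patients who are not infused.

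**The concern.** The sentence is worded for a transplant, where a conditioning regimen opens the risk period. This protocol gives induction chemotherapy or a hypomethylating agent and then cells, and it leaves later treatment to the physician. An analyst must guess the start event and is told nothing about when to stop counting.

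Take a hypothetical patient who reaches complete remission (CR) on Day 40, has an off-protocol transplant on Day 90 and dies in remission of a transplant-related infection on Day 150. The malignancy does not explain the death, so the rule scores it as treatment-related, although another treatment caused it. Section 2.2 says that transplant is typically offered to patients with some disease control, preferably in CR. Such deaths would therefore tend to fall among the patients who responded.

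Safety is the primary objective (Section 1.1), and Section 10 stresses that reinduction itself carries high mortality. Readers will look at TRM, and it should mean one thing.

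**Working it through.** The plan states no TRM rate, threshold or test, so there is no figure to reproduce. The check compares the text and then works out what each reading would count.

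**Step 1. Time windows within Section 9.0.**

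| Item | Clock starts | Clock ends |
|---|---|---|
| Failure to reach CR | start of initial induction | 60 days |
| Failure due to death | start of protocol therapy | 30 days |
| TRM | start of the preparative regimen | not stated |

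The other two items use the protocol's own start events and set limits. TRM does neither.

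**Step 2. What each reading counts.** Let *a* be the non-relapse deaths among infused patients before any off-protocol therapy, and *b* the non-relapse deaths after a later off-protocol transplant. With *n* treated, the rate is:

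- preparative regimen means induction, no end: (a + b)/n
- it means conditioning for a later transplant: b/n
- no such regimen exists, so the clock never starts: 0
- induction start, with later therapy split off: a/n

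For illustration only, assume a = 6, b = 3 and n = 60. The rates, with exact 95% intervals, are:

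- 9/60 = 15.0% (7.1 to 26.6)
- 3/60 = 5.0% (1.0 to 13.9)
- 0/60 = 0% (0 to 6.0)
- 6/60 = 10.0% (3.8 to 20.5)

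The first and last lines matter most, because both take induction as the start. They differ by b/n = 3/60 = 5.0 points, purely from the missing end.

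**Step 3. Weight of one death.** 100/n gives 100/60 = 1.7 points at the current cord blood unit (CBU) cohort target, 100/35 = 2.9 at the 2017 target and 100/20 = 5.0 at the initial cohort size.

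**Step 4. Possible scale of *b*.** The documents give no rate of later transplant and no mortality after it. Added points = P(transplant) × P(non-relapse death after transplant). Assuming 10–30% for each:

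- low: 0.1 × 0.1 = 1 point, 0.6 of 60 patients
- middle: 0.2 × 0.2 = 4 points, 2.4 of 60
- high: 0.3 × 0.3 = 9 points, 5.4 of 60

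The nearest figure in the documents is the second-salvage series in Section 2.1, where 74 of 594 patients (12.5%) had an allogeneic transplant as salvage. Using that as a stand-in with the same assumed 10–30% mortality gives 1.2 to 3.7 points, or about 0.7 to 2.2 deaths in 60. Deaths caused by non-transplant salvage or consolidation would come on top.

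**Step 5. Denominator.** An infused patient cannot have died before infusion. With uninfused patients replaced, deaths between the start of induction and infusion fall outside the treated count however TRM is worded, so they need their own line.

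**The case against.** The strongest objection is that a sensible reader resolves the start without trouble. Induction is the only regimen given before the graft, so it is the natural meaning of preparative regimen. This stands. A reader might infer that the rule misses induction deaths, but that requires taking the term to mean conditioning for a later transplant, or holding that the clock never starts. In the second case later transplant deaths are missed too. Nor can I exclude a use of the term in the opening of the schema or in Section 2.6, which were not in the text available to me. None of this supplies an end to the window.

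Second, a reader might infer that TRM is the only mortality measure. It is not. Section 9.0 has a treatment-failure category with the criterion "Patient died within 30 days of starting protocol therapy", Section 8.3 requires immediate reporting of fatal events, and Section 10.2 pauses the study for a death directly attributed to the infusion. However, the 30-day category includes deaths with persistent leukemia, and a septic death on Day 45 without leukemia fits neither treatment-failure subtype. TRM is the only non-relapse mortality measure that Section 9.0 defines.

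Third, no planned decision uses TRM. It is absent from the objectives, the primary safety definition in Section 10, the sample size and the stopping table. This stands and limits the importance of the point.

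Fourth, Section 7.4 does not name transplant, and the scale above rests on assumed rates. Section 2.2 says transplant suits only a minority, and Section 2.1 tabulates CR/CRp rates from none to 30% after failure of hypomethylating agents. A 30% transplant rate would therefore need nearly all responders at the top of that range to be transplanted, unless the cells raise response. The upper end of the range should be read with that in mind.

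**Conclusion.** The point holds in a limited form. The start of TRM is named in a term that the supplied protocol text does not otherwise use, and the window has no end. Even on the natural reading, the rate adds deaths from off-protocol treatment to protocol deaths.

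The effect is on a descriptive safety figure. Its size is unknown: 1.7 points per reclassified death at 60 treated, and 1 to 9 points in total only under the assumed 10–30% ranges. The documents do not support the stronger inference that the trial's safety assessment fails because of this wording, since the primary safety definition and stopping rules do not use TRM. Correcting it will not isolate the effect of the cells either: there is no control group without cells, and the corrected rate will still combine induction toxicity with cell toxicity. The correction yields a rate that two analysts would compute alike and that does not charge later treatment to the protocol.

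**What to change.** Replace the sentence in Section 9.0 with a definition along these lines: among infused patients, TRM is death at any time after the start of protocol induction therapy that persistent, relapsed or progressive disease does not explain. Report it on two lines:

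- deaths before any off-protocol anti-leukemia therapy or transplant
- deaths after the start of such therapy, listed by the therapy they followed

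Keep any death attributed to the infused cells, such as fatal GVHD, on the first line whenever it occurs. State beforehand which attribution categories of Section 8.2 qualify. List deaths between the start of induction and infusion separately, because those patients are replaced.

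Do not close the window at a fixed day. Day 60 would match the response assessment but would drop later fatal GVHD, the main risk attributable to the cells. Section 7.1 continues GVHD assessment to one year when there is donor chimerism, Section 5.5 links complete, durable chimerism to severe acute GVHD, and Section 8.3 provides for fatal chronic GVHD.

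The cost is a reworded definition, one extra line in the results plus the short pre-infusion list, and possibly one data field: Sections 7.4 and 11.1 plan follow-up of survival and disease status but do not say that the date of next therapy is collected. Treatment does not change, and every death remains visible.

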10. STATISTICAL CONSIDERATIONS

The primary objective of this study is to evaluate the safety of adoptive immunotherapy with IPA targeted CBU or with haplo-identical stem cells after conventional induction therapy for very high risk AML or MDS.

The study has 2 cohorts. Patients in cohort 1 will receive CBU cells as adoptive immunotherapy. Patients in cohort 2 will receive haplo identical cells. Both cohorts will be evaluated separately and no formal statistical comparison between cohorts will be performed in this pilot study.

Reinduction therapy in patients with recurrent AML and MDS is extremely toxic with high induction related mortality, which is however justified by the dismal prognosis of patients who don't receive treatment. Safety of the adoptive immunotherapy will be defined as absence of life threatening complications attributable to the adoptive immunotherapy part of the protocol. These are restricted to: 1) grade III-IV GVHD; an incidence of $>10\%$ of this complication in either cohort will be considered unacceptable. 2) Unexplained prolonged myelosuppression, i.e. no count recovery for more than 30 days after completion of chemotherapy, without evidence of residual or recurrent leukemia/MDS. An incidence of $>10\%$ of this complication will also be considered unacceptable.

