2.5 Rationale for the Current Study: Potential Risks

The risks of adoptive cell therapy include the development of graft vs host disease, prolongation of myelosuppression and development of donor specific antibodies that may interfere with further therapy. A syndrome akin to engraftment syndrome, but seemingly mediated by other cytokines and labeled “haplo-immunostorm” has also been described.¹³ Based on preliminary experience by others, we believe that such risks are extremely low.¹⁴ Nevertheless, a major goal of the proposed studies is to detect toxicities and stopping rules are incorporated in case of excessive toxicity.

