8.3 Recording and Reporting of Adverse Events and SAEs

- Safety reporting will be 21 CFR 312.32 compliant.
- Salvage chemotherapy for AML/MDS is a complex procedure with the possibility of prolonged initial admission and numerous immediate and delayed complications as well as frequent readmissions.
- **Expected toxicities are those listed in the consent form and include regimen-related toxicities, myelosuppression, opportunistic infections, haplo-immunostorm, engraftment syndrome and GVHD. These will be captured in the transplant database and reported to the IRB on a quarterly basis**
- **Unexpected** adverse events are those leading to ICU admission or to death. Such toxicities will be reported immediately to the designated study chairman. Such events will be reported to the local IRB within the institution's prescribed time period.

	Immediate Reporting	Report quarterly
Hematopoietic Toxicity	Death	Time to Hematopoietic recovery
Extramedullary Toxicity	Fatal toxicity and toxicity requiring ICU admission	Grade III-IV toxicities not requiring ICU admission
Infections	Fatal or requiring ICU admission	Grade II-IV
Acute GVHD	Fatal or Grade IV	Grade II-IV
Chronic GVHD	Fatal or requiring ICU admission	Limited and extensive
Haplo-immunostorm and/or engraftment syndrome	Fatal or requiring ICU admission	All others.

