10.1 Sample Size Considerations

With a sample size of approximately 20 patients in each cohort, a 95% confidence interval for the proportion of patients experiencing grade III-IV GVHD complications or unexplained prolonged myelosuppression complications in each cohort can be constructed to be within \pm 13.1% of the observed complication proportions. This calculation assumes an expected prevalence of each of these complication proportions of $\leq 10\%$.

Addendum November 2017 Extension of the UCB cohort

The preliminary results in the UCB cohort are encouraging (section 2.6). We therefore have increased accrual to this cohort to a total of **35 patients treated**. This will allow a preliminary assessment of efficacy. Patients who are enrolled but do not undergo treatment (defined as infusion of stem cell product) will be replaced.

Addendum May 2020: In order to further solidify outcomes in the CBU cohort and pending completion of next protocols, we will further increase accrual to this cohort to a total of **60 patients treated**. This will allow a definitive assessment of efficacy. Patients who are enrolled but do not undergo treatment (defined as infusion of stem cell product) will be replaced.

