10.2 Stopping Rules

The occurrence of adverse events that are life-threatening, lead to ICU admission or death (as defined in section 8.3) will lead to temporary suspension of enrollment and immediate assessment of events.

The study will also be paused if there is death that is directly attributed to infusion of adoptive cell therapy; for example severe infusion related reaction, infection from contaminated unit, Grade 5 GVHD etc.

Enrollment may resume upon assessment by the investigators that there are no safety issues and upon appropriate revision of the protocol – if required.

After 10 patients are enrolled in each group, the incidence of the above-defined life-threatening complications will be assessed. If more than one patient out of 10 enrolled patients (i.e., $>10\%$) in a cohort experiences either of these complications, the cohort will be stopped for safety. Each cohort will be evaluated separately with respect to these complications. Additionally, if three or more of the first five patients in a particular cohort experiences either of these complications, the cohort will also be stopped. This is illustrated in the Table below.

N treated subjects	5	10	15	20
No with gr III-IV GVHD to trigger stopping rules	2	2	3	4
No with prolonged myelosuppression to trigger stopping rules	2	2	3	4
No with either Gr III-IV GVHD or with prolonged myelosuppression to trigger stopping rules	3			

For assessment of secondary objectives, descriptive statistics will be utilized via the method of binary proportions and 95% confidence intervals will be calculated to assess the precision of the obtained estimates. All analyses will be performed in SAS Version 9.3 (SAS Institute, Inc., Cary, NC) and Stata Version 13.0 (StataCorp, College Station, TX).

Addendum 5/26/2020: To date stopping rules have not been met in the CBU cohort after enrolling more than 30 patients. The Haplo cohort has not accrued.

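### The primary safety definition is closed at two complications, so severe haplo-immunostorm/CRS and non-GVHD infusion deaths fall outside the endpoint, its 10% limits and the stopping counts

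*Combined protocol and SAP*

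**What the plan says.** Section 10 gives the operative definition. Safety is the absence of life-threatening "complications attributable to the adoptive immunotherapy part of the protocol. These are restricted to" two items:

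- Grade III-IV GVHD. An incidence above 10% "of this complication in either cohort will be considered unacceptable".
- Unexplained prolonged myelosuppression, meaning "no count recovery for more than 30 days after completion of chemotherapy, without evidence of residual or recurrent leukemia/MDS". The same 10% limit applies.

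Section 10.1 sizes the cohorts on these two events only. The stopping table in Section 10.2 has rows for each of the two and for either of them, and no others.

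Other sections recognise further harms of the cells:

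- Section 2.5 lists among the risks of the cell therapy "A syndrome akin to engraftment syndrome, but seemingly mediated by other cytokines and labeled" haplo-immunostorm.
- Section 5.5 (modified May 2020) defines that syndrome as lacking histological evidence of GVHD. It is graded like cytokine release syndrome (CRS), with a grade 5 for death.
- Section 8.3 has a reporting row for "Haplo-immunostorm and/or engraftment syndrome": immediate if fatal or requiring ICU admission, otherwise quarterly.
- Section 10.2 adds: "The study will also be paused if there is death that is directly attributed to infusion of adoptive cell therapy". Its examples are a severe infusion reaction, infection from a contaminated unit, and grade 5 GVHD.

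**The concern.** The first half of the definition would take in a grade 4 immunostorm or a fatal infusion reaction: each is life-threatening and attributable to the cells. The second half shuts them out. Immunostorm cannot enter through the GVHD item, because Section 5.5 defines it by the absence of histological GVHD.

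Safety is the primary objective. A cohort could therefore have several such events and still satisfy the written definition of safe. The reverse also matters: if none occurred, the plan does not ask for the interval that would make that a reportable safety finding.

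**Working it through.** **1. The plan's own figure.** Section 10.1 states: "With a sample size of approximately 20 patients in each cohort, a 95% confidence interval for the proportion of patients" affected lies within 13.1 percentage points. It adds: "This calculation assumes an expected prevalence of each of these complication proportions of" at most 10%. With n = 20 and p = 0.10, the Wald half-width is 1.96 × √(0.10 × 0.90 / 20) = 0.1315, which agrees with the stated figure to rounding. At the current CBU target of 60 the same formula gives 1.96 × √(0.09 / 60) = 0.076. There is no arithmetic error. The figure simply concerns the two listed events.

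**2. Where each event counts.**

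| Event | Primary proportion and 10% limit | Stopping table | Pause (10.2) | Immediate report (8.3) |
|---|---|---|---|---|
| Grade III-IV GVHD | Yes | Yes | If life-threatening, ICU or fatal | If grade IV or fatal |
| Prolonged myelosuppression | Yes | Yes | If life-threatening, ICU or fatal | If fatal |
| Severe haplo-immunostorm/CRS | No | No | If life-threatening, ICU or fatal | If ICU or fatal |
| Non-GVHD death attributed to infusion | No | No | Yes | Yes |

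Treatment-related mortality is defined in Section 9 but has no limit and no place in the primary definition.

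**3. Effect on the primary rates.** Assume GVHD and myelosuppression each occur in 5% of patients, the omitted event in a fraction c, and all three independently. The documents give none of these rates.

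- c = 10%: any of the three = 1 − 0.95 × 0.95 × 0.90 = 18.8%.
- c = 20%: any of the three = 1 − 0.95 × 0.95 × 0.80 = 27.8%.

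In both cases each listed event stays at 5%, under its limit.

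**4. Effect on the count-based rule.** Let s(p) be the chance that one row crosses 2 of 5, 2 of 10, 3 of 15 or 4 of 20 at any look. Exact binomial calculation gives s = 9.6%, 31.4%, 74% and 94% at p = 5%, 10%, 20% and 30%. The three-of-five rule for either event adds nothing: three affected patients among five must include at least two with the same complication, which already crosses a row.

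- As written, with both listed events at 5%: 1 − (1 − 0.096)² = 18%, whatever the value of c.
- For comparison, a hypothetical third row with the same counts: 1 − 0.817 × (1 − s(c)) = 26%, 44%, 79% and 95% at c = 5%, 10%, 20% and 30%.

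The comparison shows only that the written rule does not respond to the omitted events. The tabulated looks end at 20, and the May 2020 addendum says more than 30 CBU patients had been enrolled. For that cohort the live consequence is therefore the final safety statement.

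**5. What an interval would say at n = 60 (Clopper-Pearson).** Six events: 10.0%, 95% CI 3.8% to 20.5%. No events: upper bound 1 − 0.025^(1/60) = 6.0%. These are illustrations. Six of 60 is exactly 10% and would not exceed a limit worded as above 10%.

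**The case against.** The restriction is reasoned. Section 10 explains that reinduction is itself very toxic, and Sections 8.1 and 9 name essentially the same two complications as the ones attributable to the cells. Fever, hypotension and hypoxia after reinduction are hard to assign to the infusion, and the CRS table counts them only if no other cause explains them. Choosing more clearly attributable events is defensible. It does not explain why harms the protocol itself calls attributable are left out of a definition built on attribution.

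A reader might infer that these events cannot count against safety at all. The documents do not support that:

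- Any life-threatening, ICU-level or fatal event suspends enrollment, a more sensitive trigger than a 10% limit.
- Enrollment resumes only after the investigators assess that there are no safety issues, with protocol revision if required.
- Fatal or ICU-level immunostorm is reported immediately.
- All adverse events go to the DSMB after every five patients per arm, and it may recommend termination.

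It would also be too broad to say that all infusion-attributed deaths are excluded. A death from GVHD scored grade III-IV already counts.

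What remains is narrower. The pause has no count or rate and is lifted on the investigators' own assessment. Neither it nor the reporting changes the primary proportion or the criterion for calling a cohort safe. A grade 3 immunostorm managed without ICU admission and not judged life-threatening might trigger no pause and would be reported quarterly.

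The likely frequency is also fairly disputed. Section 2.5 believes the risks extremely low, and the haplo cohort, where the syndrome was first described, had not accrued by May 2020.

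**Conclusion.** The point holds as an inconsistency between the definition of safety and its closed list. Severe haplo-immunostorm/CRS and non-GVHD infusion-attributed deaths are monitored, but they are excluded from the primary endpoint, the 10% limits and the count-based stopping rule. This rests on the text and needs no assumption about rates.

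The size does need one. The available text gives no rate for these events, and the preliminary results in Section 2.6 could not be consulted. The 18.8%, 27.8% and 6-of-60 figures show what the plan would not register. They do not predict what will happen. A reader might conclude that the trial's safety conclusion will be wrong, but the documents do not support that: if the omitted events are as rare as Section 2.5 expects, the conclusion would hardly change. The plan should be amended so that the conclusion matches its own definition either way.

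**What to change.** 1. Reconcile Sections 2.5, 5.5, 8.3, 10 and 10.2 on which complications are attributable to the cells. Include the mismatch between grade 5 GVHD in Section 10.2 and grade III-IV in Section 10.
2. Add a third component to the Section 10 list: grade 3 or higher haplo-immunostorm, CRS or engraftment syndrome, or any non-GVHD death attributed to the cell infusion. State which attribution categories from Section 8.2 qualify.
3. Report it per cohort with an exact 95% confidence interval beside the other two, and within a descriptive any-complication proportion. Require the safety conclusion to take it into account.
4. Leave the existing stopping boundaries unchanged. Section 10.2 applies its ten-patient rule to the complications defined above it, so say explicitly that the third component is reported and does not enter those counts.

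The cost is mainly wording. Weekly GVHD and engraftment-syndrome assessment and adverse event attribution are already planned. There are two downsides: the stated complication rate may be less favourable, and patients treated before the May 2020 CRS grading text may need to be graded from their records. The amendment should say that the component was added after more than 30 CBU patients had been enrolled.
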